# ABBREVIATIONS

**ALI** = Acute Lung Injury  
**ARDS** = Acute Respiratory Distress Syndrome  
**BAL** = Bronchoalveolar lavage  
**BMI** = Body Mass Index  
**BUN** = Blood Urea Nitrogen  
**CHF** = Congestive Heart Failure  
**CPAP** = Continuous Positive Airway Pressure  
**Cst** = Static compliance  
**Cdyn** = Dynamic compliance  
**C20** = change in compliance over the last 20% of inspiration  
**CT** = Computed Tomography  
**DBP** = Diastolic Blood Pressure  
**DSMB** = Data Safety Monitoring Board  
**ECMO** = Extracorporeal Membrane Oxygenation  
**EIT** = Electronic Impedance Tomography  
**FiO2** = Fraction of Inspired Oxygen  
**GCS** = Glasgow Coma Scale  
**IBW** = Ideal body weight  
**ICU** = Intensive Care Unit  
**IL-6** = Interleukin 6  
**IL-8** = Interleukin 8  
**INR** = International Normalized Ratio  
**LAR** = legally authorized relative  
**LTAC** = Long Term Acute Care facility  
**mBW** = measured body weight  
**OR** = Odds Ratio  
**P/F** = PaO2/FiO2 ratio  
**PaCO2** = Partial pressure of arterial carbon dioxide  
**PaO2** = Partial pressure of arterial oxygen  
**PAP** = Pulmonary Artery Pressure  
**PB** = Barometric Pressure

**PBW** = Predicted Body Weight  
**PEEP** = Positive End-Expiratory Pressure  
**PI** = Principal investigator  
**PIN** = Personal Identification Number  
**Pmean** = Mean airway pressure  
**Ppeak** = Peak airway pressure  
**Pplat** = Plateau pressure  
**PS** = Pressure Support Ventilation  
**RASS** = Richmond Agitation Severity Score  
**SBP** = Systolic Blood Pressure  
**S/F** = SpO2/FiO2 ratio  
**SP-D** = Surfactant protein D  
**SpO2** = Oxygen Saturation  
**sRAGE** = Soluble Form of Receptor for Advanced Glycation End Products  
**TNFR1** = Tumor necrosis factor receptor 1  
**VAP** = Ventilator-associated Pneumonia  
**VFD** = Ventilator-free Days  
**VWF** = Von Willebrand Factor  
**WBC** = White Blood Cell

# DEFINITIONS

**Controlled Ventilation:** Any mode with a backup rate and which allows clinicians to either set tidal volume to a target or adjust pressures to target a tidal volume. Examples include volume assist control, pressure assist control, pressure regulated volume control.

**Study withdrawal:** Defined as permanent withdrawal from study before completion of study activities. This does not include those subjects who have completed the protocol procedures or stopped procedures because they have reached unassisted breathing. If a patient or surrogate requests withdrawal from the study the clinician should seek explicit permission to continue data collection.

**Invasive Mechanical Ventilation:** Assisted ventilation delivered by a nasotracheal, orotracheal, or tracheostomy tube

**Legal Representative:** An individual, judicial, or other body authorized under applicable law to consent on behalf of a prospective patient to the patient's participation in the clinical study.

**Study Day:** The day of randomization is study day zero. The next day is study day one.

# Use of Electrical Impedance Tomography for Optimization of Positive End-Expiratory Pressure in Acute Respiratory Distress Syndrome

## 1 Background

Acute respiratory distress syndrome (ARDS) is a common condition in the intensive care unit [1] which requires invasive mechanical ventilation. Because the administration of mechanical breaths from the ventilator can exacerbate lung injury, patients with ARDS are treated with lung protective ventilation (LPV), which entails providing a low tidal volume in order to maintain a plateau pressure under 30 cm H2O [2]. LPV decreases lung inflammation as a means of improving outcomes [2,3]. In ARDS, the distribution of delivered gas via mechanical ventilation is heterogeneous: there are areas of atelectatic lung which are not ventilated and this accounts for the refractory hypoxemia seen in ARDS.

Efforts to recruit areas of atelectatic lung via the administration of a high positive end-expiratory pressure (PEEP) have been employed in an attempt to further improve the outcome of patients with ARDS; but this has met with mixed results [4,5]. On a breath by breath basis, during mechanical ventilation with ARDS and PEEP some areas of the lung may become over-distended, ostensibly worsening lung injury, a phenomenon called tidal hyperinflation [6]. In addition, patients with ARDS receiving LPV can develop ventilator asynchrony which results in the intermittent development of potentially injurious large tidal volumes [7,8].

In ARDS, there is also heterogeneity between patients: some patients respond to PEEP with recruitment of atelectatic lung regions and improvement in gas exchange while others do not [9]. Ideally, mechanical ventilation in ARDS patients would be individualized such that the right amount of airway pressure is applied to each patient, maximizing recruitment while avoiding potentially harmful over-distension and tidal hyperinflation.

At present, it is unknown how to make the best tradeoff between lung recruitment and over-distension. The best work in this area has been performed utilizing CT scanning, a tool not routinely available to clinicians [9,10]. The work of Chiumello, using CT scanning, has suggested the best tradeoff among four different approaches to mechanical ventilation in ARDS is the PEEP table utilized in the Canadian LOVS trial [10,11].

Electrical impedance tomography (EIT) offers an opportunity to evaluate regional lung ventilation at the patient's bedside [12-14]. Although EIT has been utilized to assess the distribution of lung ventilation in ARDS patients, large clinical trials are lacking. Single-center pilot studies are insufficient to make a determination regarding whether ventilator optimization via EIT improves clinical outcomes. Lung protective ventilation

results in some mitigation of lung inflammation and can be a useful surrogate endpoint in smaller trials [3,15]. Bronchoalveolar lavage specimens obtained from intubated patients with ARDS are studied for biomarkers of lung inflammation which reflect the relative success or failure of different forms of mechanical ventilation to protect the lung from additional injury.

## 1.1 STUDY RATIONALE

To date, studies of EIT in ARDS patients have only assessed the distribution of ventilation and not whether lung inflammation is decreased. Our research goals are to assess markers of lung inflammation: IL-6, IL-8, TNFR1, sRAGE, SP-D, Angiopoentin-2, and VWF in conjunction with ventilator changes made in ARDS patients correlated with EIT in order to determine whether the optimization of mechanical ventilation may be achieved by this means.

One arm of the protocol will have best PEEP determined by oxygenation response using a PEEP/FiO2 combination table, similar to the one used in the LOVS protocol [11]. A modified version of the LOVS's table (High-PEEP) has been incorporated into the University of Michigan ARDS protocol. EIT findings will be determined but the bedside respiratory therapist will be blinded to the EIT findings during this arm of the protocol. Alternatively, in the second arm of the protocol, EIT will be used to determine the best PEEP – i.e. the PEEP level at which recruitment is maximized and over-distension minimized. Lung inflammatory markers obtained at 6 hours post recruitment via EIT will be compared with markers obtained 6 hours after the time when PEEP had been guided by the High-PEEP table. In addition, following crossover to the opposite group, biomarkers will be obtained after an additional 14 to 18 hours.

# 2 Objectives

## 2.1 Primary Objective

- To compare the effect of EIT in patients with moderate to severe and severe ARDS for the optimization of PEEP titration with standard PEEP titration using the High-PEEP table on changes in relevant physiological and biomarker outcomes.

## 2.2 Secondary Objective

- The BAL fluid will be examined for the presence of monocytes to determine whether mini-BAL is an effective method for collecting this type of specimen for future research.

## 2.3 Primary Hypothesis

- The use of electrical impedance tomography (EIT) to titrate positive end-expiratory pressure (PEEP) will result in less lung inflammation and better physiologic parameters than use of the High-PEEP table in patients with moderate to severe acute respiratory distress syndrome (ARDS).

## 3 End Points

- The protocol duration is 24 hours.

### 3.1 Physiologic Endpoints

- PaO2
- P/F ratio
- Pplat
- Driving pressure
- Cst and Cdyn
- C20/dyn

### 3.2 Biomarker Endpoints

- IL-6
- IL-8
- sRAGE
- SP-D
- Angiopoietin-2
- VWF

### 3.3 Monocyte Endpoints

- Monocyte phenotyping for HLA-DR expression
- Single cell confocal Raman microscopy of circulating and lung monocyte/macrophage
- Unbias metagenomic RNA-Seq mRNA quantitation in BAL macrophages

## 4 Study Population and Enrollment

### 4.1 Number/Source/Screening

The trial will accrue 20 patients over a 1 to 2 year interval. Patients will be recruited from the emergency departments and the critical care medicine unit (CCMU). The overall strategy is to screen and enroll early, every newly intubated, acutely ill medical patient, using clinically obtained blood gases.

### 4.2 Inclusion Criteria

1. Age  $\geq$  18 years
2. Endotracheal ventilation for  $\leq$  1 week (168 hours)
3. Presence of all of the following conditions for  $\leq$  72 hours
  - i.  $\text{PaO}_2/\text{FiO}_2 < 150$  with  $\text{PEEP} \geq 5 \text{ cm H}_2\text{O}$  for  $\geq 30 \text{ min}$ .  
OR, IF ABG NOT AVAILABLE  
 $\text{SpO}_2/\text{FiO}_2$  ratio that is equivalent to a  $\text{PaO}_2/\text{FiO}_2 < 150$  with  $\text{PEEP} > 8 \text{ cm H}_2\text{O}$  (Appendix G), and a confirmatory  $\text{SpO}_2/\text{FiO}_2$  ratio between 1-6 hours after the initial  $\text{SpO}_2/\text{FiO}_2$  ratio determination
  - ii. respiratory failure not fully explained by cardiac failure or fluid overload

4. Bilateral opacities not fully explained by effusions, lobar/lung collapse, or nodules for  $\leq$  1 week (168 hours)
5. All criteria listed in (3) developed within 1 week of a known clinical insult or new or worsening respiratory symptoms

The 72-hour enrollment time window begins when criteria 1-4 are met. Criteria may be met at either the University of Michigan Hospital or a referring hospital.

#### **4.3 Exclusion Criteria**

1. Lack of informed consent
2. Known pregnancy
3. ECMO
4. Severe chronic respiratory disease requiring home oxygen therapy or ventilation
5. Calculated BMI of greater than 50
6. Severe chronic liver disease defined as a Child-Pugh score of 12-15
7. Prior bone marrow transplantation or present chemotherapy induced neutropenia
8. Expected duration of mechanical ventilation of < 48 hours
9. Decision to withhold life-sustaining treatment
10. Moribund patient not expected to survive 24 hours
11. Diffuse alveolar hemorrhage from vasculitis
12. Burns > 40% total body surface or burns on the thorax
13. Unwillingness to utilize the ARDS Network 6 ml/kg IBW ventilation protocol
14. Neurologic conditions with risk of intracranial hypertension
15. ARDS criteria met for > 48 hours
16. Contraindications to using EIT (Presence of a pacemaker or AICD, inability to place the belt (presence of surgical wounds dressing, thoracic or spinal cord trauma, recent thoracic surgery, etc), undrained pneumothorax or BPF)
17. Platelet count < 50 K/uL

See Appendix A for specific exclusion criteria definitions.

#### **4.4 Randomization, and Study Initiation Time Window**

All patients must be randomized within 72 hours of meeting inclusion criteria. The window for randomization begins at the time of meeting all inclusion criteria, regardless of patient location.

#### **4.5 Informed Consent**

Informed consent will be obtained from each patient or legally authorized representative (LAR) prior to enrollment in the trial. No study procedures will be done prior to obtaining informed consent.

Permission to approach patients and/or LARs will be requested from the attending physicians. All patients meeting inclusion criteria will be entered on a screening log. If the patient is not enrolled, the screening log will include information explaining why

enrollment did not occur (e.g., exclusion criteria, attending physician denial, patient refusal).

## **4.6 Randomization**

Randomization assignment will be made via sealed envelopes. Twenty envelopes have been prepared containing the randomization selection – ten stating “EIT first” and ten stating “Usual Care First.” These envelopes have been shuffled and stored in a larger envelope. After obtaining a signed and dated informed consent, a sealed envelope will be selected and opened to reveal the randomization assignment.

# **5 Study Procedures**

## **5.0 Study Design:**

Single-center, prospective, 2-arm, unblinded, randomized, cross-over clinical trial.

### **5.1. Study Initiation**

At the time of randomization all study subjects will be receiving the standard University of Michigan ARDS protocol high PEEP arm (Appendix B). All patients will receive lung protective ventilation (LPV), attempting to achieve a plateau pressure (Pplat)  $\leq$  30 cm H2O with tidal volume by ideal body weight being allowed as high as 8 cc/kg and as low as 4 cc/kg in so doing.

Following randomization patients will undergo a mini-BAL according the methodology undertaken by Ranieri and colleagues [16] prior to institution of the protocol arm.

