## 6.2 Baseline Assessments

The following information will be recorded during the 24-hour interval preceding randomization. If more than one value is available for this 24-hour period, the value closest to the time of randomization will be recorded. If no values are available from the 24 hours prior to randomization, then values will be measured post randomization but prior to study initiation.

1. History and physical examination
2. Vital signs: heart rate (beats / min), systemic systolic and diastolic BP (mmHg), body temperature (°C)
3. Ventilator mode, rate, minute ventilation, tidal volume, FiO2, PEEP, Pplat, Ppeak, and Pmean
4. Arterial blood gas (PaO2, PaCO2, SaO2, pH) and SpO2
5. Frontal Chest Radiograph – radiographic lung injury score (# of quadrants)
6. Administration of the following medications (name)
  - (a) Sedatives
  - (b) Analgesics
  - (c) Vasopressors
  - (d) Corticosteroids
7. Presumed site of infection, if sepsis is the etiology of ARDS
8. APACHE II score, including the acute physiology components
9. APACHE II demographics plus history of: hypertension, prior myocardial infarction, congestive heart failure, peripheral vascular disease, prior stroke with sequelae, dementia, chronic pulmonary disease, arthritis, peptic ulcer disease
10. SOFA Score: Cardiovascular, renal, respiratory, hepatic, and hematology organ function will be assessed using the SOFA methodology as described in Appendix H.

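### The baseline mini-BAL follows the opening of the envelope in an unblinded trial, so whether and how the only baseline biomarker sample is obtained is decided with the sequence known

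*Combined protocol and SAP*

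**What the plan says.** - Section 5.0 describes the trial as "Single-center, prospective, 2-arm, unblinded, randomized, cross-over clinical trial".
- Section 4.6: "After obtaining a signed and dated informed consent, a sealed envelope will be selected and opened to reveal the randomization assignment". The supply is fixed: "Twenty envelopes have been prepared containing the randomization selection", ten for each sequence. Section 4.1 matches it: "The trial will accrue 20 patients over a 1 to 2 year interval".
- Section 5.1: "Following randomization patients will undergo a mini-BAL according the methodology undertaken by" a cited study, "prior to institution of the protocol arm". Sections 5.1.3 and 5.1.4 both start their arm's procedures once this lavage is complete.
- Section 5.1.2 bars the lavage at P/F below 100 (or an imputed S/F below 89) and stops it for sustained desaturation. Local anesthesia is left to the clinician or therapist.
- Section 2.1 states the primary objective in terms of changes in physiological and biomarker outcomes. Section 7 compares the groups at baseline, at 6 hours and at the end of the protocol.
- Appendix F places the first lavage before the first PEEP setting but does not show when randomization happens.

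**The concern.** A baseline measurement is best protected when it is complete before anyone knows the assignment. Here the one baseline sample for the biomarkers is collected afterwards, by unblinded staff. No passage blinds the person doing the lavage or the laboratory. The only blinding mentioned (section 1.1) keeps EIT findings from the bedside therapist in the table arm.

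Two things are at stake. First, the choices left open in the lavage could in principle differ by sequence. Second, and more important, a lavage that is withheld or stopped becomes a post-randomization event. A change-from-baseline analysis restricted to patients with a baseline sample would then select on something that could depend on assignment. At about ten patients per sequence, a few such cases matter.

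**Working it through.** **1. Order of steps.** Sections 4.6 and 5.1 read together give: consent, envelope opened, first lavage, PEEP set. Appendix F agrees on lavage before PEEP and is silent on the envelope, so it neither contradicts nor repairs this order.

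**2. What is open to judgement.** Fixed in 5.1.2: numeric limits for withholding and stopping, aliquot volumes, the trigger for a third lavage, and a radiograph rule for site. Left open: the increase in sedation, optional lidocaine, right middle versus lower lobe, and the reading of infiltrates as diffuse or localized. The section also does not say which P/F or S/F reading governs the limit.

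**3. How a baseline sample can be lost.** Entry (4.2) needs P/F below 150 and sets no lower limit, and 2.1 includes severe ARDS. The lavage is barred below 100. A patient can therefore be eligible, randomized and then barred. A started lavage can also be stopped. The platelet bar adds little, because 4.3 already excludes counts below 50 K/uL. No passage replaces such patients, adds envelopes or says how they are analysed.

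**4. How often.** The plan's 20 patients come with no alpha, power, effect size, SD or loss rate, so there is no calculation to reproduce. Let q be the assumed share of randomized patients without a baseline lavage. The expected number is 20q, and the chance of at least one is 1 − (1 − q)^20:

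- q = 10%: 2 patients; 1 − 0.9^20 = 88%
- q = 20%: 4 patients; 1 − 0.8^20 = 99%
- q = 30%: 6 patients; 1 − 0.7^20 = more than 99.9%

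Losses unrelated to sequence still disturb the 10/10 split. With 4 lost, an even split has probability C(10,2)² / C(20,4) = 2025/4845 = 42%, so the sequences differ by 2 or more with probability 58%.

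**5. Precision of an analysis that needs the baseline sample.** Assume a two-sample t-test, two-sided 0.05 and 80% power. Solve for d in P(T > t₀.₉₇₅ with 2n − 2 df) = 0.80, where T is noncentral t with noncentrality d√(n/2).

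| n per sequence | df | critical t | d (SD) |
|---|---|---|---|
| 10 | 18 | 2.101 | 1.32 |
| 9 | 16 | 2.120 | 1.41 |
| 8 | 14 | 2.145 | 1.51 |
| 7 | 12 | 2.179 | 1.63 |

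These rows apply to a baseline or change-from-baseline biomarker analysis. The 6-hour comparison in section 7 needs the second lavage, and nothing bars that lavage because the first was withheld.

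**6. Timing of the second lavage.** Sections 5.1.3 and 5.1.4 count about six hours from randomization. Section 6.3 and Appendix F count six hours from established PEEP. With the envelope opened first, the two anchors differ by at least the lavage time (about 30 minutes, Appendix F) plus the time to set PEEP (20–40 minutes with EIT, 5–10 with the table): at least 50–70 minutes in one sequence and 35–40 in the other.

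**The case against.** The strongest reply is that little harm can follow. At randomization every patient is on the same High-PEEP protocol, and the first lavage precedes any arm-specific PEEP. The catheter is advanced blindly, volumes are set, and the limits for withholding and stopping are numeric. The envelope reveals only sequence, since everyone is planned to receive both methods. No mechanism is evident by which lidocaine or choice of lobe would push cytokines one way by sequence. The same knowledge exists at the second and third lavages, which resequencing leaves untouched. All of this stands, and it is why the bias is judged modest.

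It is also true that lost lavages come mainly from the mismatch between the entry range and the lavage limit, which exists whatever the order of steps.

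A reader might take the fallback in 6.2, under which missing items "then values will be measured post randomization but prior to study initiation", as permission for late biomarker baselines. It is not: 6.2 lists vital signs, ventilator settings, blood gas, radiograph, medications and scores, and no lavage biomarkers. Most of those values come from the 24 hours before randomization.

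What remains is that the present order offers no advantage, while the alternative makes availability of the baseline sample independent of assignment.

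**Conclusion.** The order of steps is certain from the text, and it should be changed. Its consequence is limited. The baseline biomarker sample, and its absence, are determined with the sequence known, so a change-from-baseline comparison among patients who have the sample is not protected by randomization.

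Three stronger conclusions might be inferred, and the documents do not support them:

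- That baseline samples will in fact be biased. The text shows opportunity only.
- That the trial's power falls to 1.51–1.63 SD. The losses of 2 or 3 per sequence, the alpha and the power are all assumed. The figures do not describe the 6-hour between-group test, and physiologic endpoints do not depend on the lavage.
- That moving the lavage would save the envelopes. If an envelope is still opened after a withheld lavage, the number of patients without a baseline sample is unchanged. Only its independence from assignment improves.

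**What to change.** - Amend 4.6 and 5.1, and mark randomization in Appendix F, so that the order is: consent; baseline assessments; first mini-BAL attempted and its outcome recorded (completed, withheld or terminated, with the reason); envelope opened; PEEP set.
- In 5.1.3 and 5.1.4, replace the randomization anchor for the second lavage with the one defined in 6.3, six hours from established PEEP.
- Separately, the sponsor must reconcile the entry range in 4.2 with the lavage limit in 5.1.2 and 9.1. No threshold is proposed here.

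**Cost.** A protocol amendment, with no added procedure: every patient is already due this lavage after consent and before arm-specific PEEP. Assignment is known about 30 minutes later, and the lavage must fit inside the 72-hour randomization window. An occasional consented patient may be lavaged, with the risks listed in 9.1, and then not randomized.

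Randomizing only patients with a completed baseline lavage would be a different and costlier rule. To reach 20 it would need 20/(1 − q) consented patients, rounded up: 23, 25 or 29 at assumed q of 10%, 20% or 30%. It would also leave out patients below the lavage limit although the objective includes severe ARDS. It is not needed for this correction.

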#### **5.1.2 Mini-BAL Procedure**

After the administration of sedation, consisting of an increase in the baseline amount of propofol or midazolam already being administered, local anesthesia will be administered by instilling 1-3 cc aliquots of 2% lidocaine via the endotracheal tube port. The use of local anesthesia is optional and will only be administered if deemed necessary by the clinician or RT.

1. FiO2 will be increased to 1.0 ten (10) minutes prior to the start of the procedure.
  - Mini-BAL will not be performed if the P/F ratio is < 100 or the imputed S/F (Appendix G) ratio is less than 89. [17]
  - Mini-BAL will not be performed if the platelet count < 50 K/uL.
2. Sedation with appropriate increases in propofol or midazolam will be made prior to insertion of the catheter.
3. When diffuse infiltrates are seen on chest radiography, the mini-BAL catheter will be directed toward the right middle or lower lobes. When an area of localized pulmonary infiltrate is present the mini-BAL catheter will be directed toward the lower lobe of the opposite lung.
4. A Halyard mini-BAL catheter will be inserted into the endotracheal tube and blindly advanced to the area noted above in #3.

5. Lavage with two aliquots of 40 cc sterile isotonic saline will be performed. Fluid from the first aliquot will be discarded.
6. A third lavage will be performed if less than 30 cc is recovered from the first two aliquots.
7. The procedure will be terminated for a saturation <89% for >1 minute following the administration of any aliquot.
8. The non-discarded BAL fluid will be put on ice and transported to [name] laboratory for cytokine for IL-6, IL-8, TNFR1, sRAGE, SP-D, Angiopoentin-2, and VWF.

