### 9.1 Risks of mini-BAL

Study subjects will be assessed before, during and for 15 minutes after the mini-BAL. Potential complications of the Mini-BAL procedure include pneumothorax, bronchial hemorrhage, vagal reflex, bronchial irritation, and transient arterial hypoxemia. Prior to performing mini-BAL the study subject's FiO2 will be increased to 1.0 ten (10) minutes prior to the start of the procedure. Mini-BAL will not be performed if the P/F ratio is < 100 or the imputed S/F ratio is less than 89. Mini-BAL will not be performed if the platelet count < 50 K/uL. During performance of the mini-BAL the procedure will be terminated for a saturation <89% sustained for greater than 1 minute following the administration of any aliquot. The early termination of the mini-BAL, based on the above criteria, will be reported as an adverse event.

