### **9.6 Risks in Relation to Anticipated Benefits**

Federal regulations at 45 CFR 46. 111 (a)(2) require that “the risks to subjects are reasonable in relation to anticipated benefits, if any, to subjects, and the importance of the knowledge that may reasonably be expected to result.” Based on the preceding assessment of risks and potential benefits, the risks to subjects are reasonable in relation to anticipated benefits.

**Procedures** – Mini-BAL can result in transient worsening of hypoxemia. This is usually transient in nature. Mini-BAL will not be performed for a P/F ratio  $<100$  or an S/F ratio  $<89$  and will be terminated for a S/F ratio of  $<89$  for more than one minute. Mini-BAL can result in lung irritation and bleeding. Mini-BAL will not be performed if platelets  $< 50$  K/uL.

**Treatments** – High PEEP is routinely used in clinical practice. The EIT belt is noninvasive and minimally discomforting to wear. There is potential for benefit to society and individual patients should EIT prove to be result in less lung inflammation and a large clinical trial were to demonstrate clinical benefit.

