## F. Time-Event Schedule

Clock example	Study hour	Procedures	Vent data	EIT data	HR/ BP	SpO2	ABG	Cytokines	Comments
closest	BL, pre	BL Assess	X		X	X	X		
8:00		BAL#1			X	X		X	BAL procedure time ~30 min
8:30	0	Set PEEP #1	X	X	X	X			Set EIT ~20-40 min vs table ~5-10 min
9:30	1						X	X	ABG 1 H after setting PEEP
10:30	2								
11:30	3								
12:30	4								
13:30	5								
	pre BAL	Assessment	X	X	X	X	X		
14:30	6	BAL #2			X	X		X	BAL procedure time ~30 min
15:00	0	Set PEEP #2	X	X	X	X			
16:00	1					X	X		ABG 1 H after setting PEEP
17:00	2								
18:00	3								
19:00	4								
20:00	5								
21:00	6								
22:00	7								
23:00	8								
0:00	9								
1:00	10								
2:00	11								
3:00	12								
4:00	13								
5:00	14								BAL #3, anytime between hr 14-18
6:00	15								
7:00	16								
8:00	17								
9:00	pre-BAL	Assessment	X	X	X	X	X		
9:00	18	BAL #3			X	X		X	BAL procedure time ~30 min

Data Collected:	Ventilator: mode, set VT, RRset, RRtot, VE, FiO2, PEEP, Ppeak, Pplat, Pmean, PEEPtot,
	vent calcs: drive-P, Cst, Cdyn,
	EIT: delta-EELI, ODCL; COV, GI Index, Regional compliance
	ABG: pH, PaCO2, PaO2, SaO2, BE, HCO3 (if collected for standard of care)
	Cytokines: per protocol

**Definition of Time:** Time 0 is when PEEP is established

Time 6 is 6 hours after PEEP is set

Reset time frames at cross-over

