## G. Imputed PaO2/FiO2

SpO 2	FiO 2															
	0.3	0.35	0.4	0.45	0.5	0.55	0.6	0.65	0.7	0.75	0.8	0.85	0.9	0.95	1	
80%	148	127	111	98	89	81	74	68	63	59	55	52	49	47	44	
81%	151	129	113	101	91	82	76	70	65	60	57	53	50	48	45	
82%	155	132	116	103	93	84	77	71	66	62	58	55	52	49	46	
83%	158	136	119	106	95	86	79	73	68	63	59	56	53	50	47	
84%	162	139	122	108	97	89	81	75	70	65	61	57	54	51	49	
85%	167	143	125	111	100	91	83	77	71	67	63	59	56	53	50	
86%	171	147	129	114	103	94	86	79	73	69	64	61	57	54	51	
87%	177	151	132	118	106	96	88	81	76	71	66	62	59	56	53	
88%	182	156	137	121	109	99	91	84	78	73	68	64	61	58	55	
89%	189	162	141	126	113	103	94	87	81	75	71	67	63	60	57	
90%	196	168	147	130	117	107	98	90	84	78	73	69	65	62	59	
91%	203	174	153	136	122	111	102	94	87	81	76	72	68	64	61	
92%	213	182	159	142	128	116	106	98	91	85	80	75	71	67	64	
93%	223	191	168	149	134	122	112	103	96	89	84	79	74	71	67	
94%	236	202	177	157	142	129	118	109	101	94	89	83	79	75	71	
95%	252	216	189	168	151	138	126	116	108	101	95	89	84	80	76	
96%	273	234	205	182	164	149	136	126	117	109	102	96	91	86	82	

The table is used when an ABG is not available to calculate the PaO2/FiO2. Instead, the SpO2 and FiO2 are used to impute what the PaO2/FiO2 might be. The following conditions must be met:

1. SpO2 between 80-96%
2. SpO2 should be measured at least 10 minutes after any FiO2 change
3. PEEP must be  $\geq 8$  cm H2O
4. An adequate pulse oximetry waveform tracing is present

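### The mini-BAL oxygenation gate pairs P/F <100 with an Appendix G value of 89, but Appendix G does not equate them: SpO2/FiO2 89 on FiO2 1.0 is an imputed P/F of 57

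*Combined protocol and SAP*

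**What the plan says.** Section 5.1.2 bars the lavage as follows: "Mini-BAL will not be performed if the P/F ratio is < 100 or the imputed S/F (Appendix G) ratio is less than 89". It attaches reference 17, a study on imputing P/F from SpO2/FiO2. The rule is a sub-bullet of the step in which FiO2 "will be increased to 1.0 ten (10) minutes prior to the start of the procedure". Section 9.1 repeats it: "Mini-BAL will not be performed if the P/F ratio is < 100 or the imputed S/F ratio is less than 89". Section 9.6 begins "Mini-BAL will not be performed for a P/F ratio" below 100, then gives an S/F ratio below 89 without the word *imputed*.

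Three other places bear on the meaning:

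- The abbreviation list defines S/F as "SpO 2 /FiO 2 ratio".
- Appendix G explains its purpose: "The table is used when an ABG is not available to calculate the" P/F ratio. Its output is an imputed P/F.
- Inclusion criterion 3i in section 4.2, when no gas is available, asks for an S/F "ratio that is equivalent to a" P/F below 150, by Appendix G.

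Appendix F marks a blood gas at both in-study pre-lavage assessments, but its data key takes gases only "if collected for standard of care".

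**The concern.** The second limb refers to a table that does not supply the quantity it names, and its cut-off does not correspond to the first limb on that table. A measured P/F below 100 always bars the lavage. Without a current gas, only the second limb applies, and it can admit a patient whom an equivalent measured P/F would exclude.

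This is most likely at lavages 2 and 3, where the gas depends on routine care. For lavage 1, the section 6.2 rule on baseline values largely covers the gap.

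The gate is the oxygenation safety limit for a research procedure done three times in patients enrolled at P/F below 150, and section 9.6 cites it when weighing risk against benefit. It also determines who contributes biomarker samples.

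**Working it through.** **Inputs.** The limits 100 and 89 (5.1.2, 9.1, 9.6); the definition of S/F (Abbreviations); all 17 × 15 = 255 cells of Appendix G (SpO2 80–96%, FiO2 0.30–1.0); the SpO2 floor of 88% used in 5.1.5 and 5.1.6.

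**Is the table intact?** A standard oxygen-dissociation equation (Severinghaus/Ellis form), divided by FiO2, reproduces every printed cell to within 0.5. The figure 57 is therefore not a text-extraction error.

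**Does the table give the pair 100/89?** It does not. For each cell, S/F = SpO2 (%) ÷ FiO2. At SpO2 ≥88%, the cells with imputed P/F of 98–102 have S/F from 96 ÷ 0.80 = 120 to 88 ÷ 0.55 = 160. The matching S/F changes with FiO2, so no single S/F cut-off equals P/F 100.

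**Reading 1: 89 is SpO2/FiO2.**

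| SpO2 | FiO2 | S/F | Imputed P/F | S/F limb |
|---|---|---|---|---|
| 88% | 1.0 | 88.0 | 55 | refuses |
| 89% | 1.0 | 89.0 | 57 | passes |
| 88% | 0.95 | 92.6 | 58 | passes |
| 92% | 0.80 | 115.0 | 80 | passes |

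- At SpO2 ≥88%, 66 cells have imputed P/F below 100: 10, 9, 9, 8, 8, 7, 6, 5 and 4 for SpO2 88% to 96%. Of these, 65 have S/F ≥89 and pass; only 88% on FiO2 1.0 is refused.
- The lowest S/F at SpO2 ≥88% with FiO2 below 1.0 is 88 ÷ 0.95 = 92.6, so the limb refuses nothing there.
- Over the whole table, 152 cells have imputed P/F below 100. Of these, 137 pass. The 15 refused all have imputed P/F of 55 or less.

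**Reading 2: 89 is the tabled imputed P/F.** The limits are then 89 for an imputed value and 100 for a measured one. Twenty-six cells hold 89–99, 16 of them at SpO2 ≥88%. Each passes, although the same measured P/F would be refused.

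**When is it read?** The text does not say whether before or after FiO2 goes to 1.0. Every Appendix G value in the FiO2 1.0 column lies between 44 and 82. Reading 2 applied after pre-oxygenation would therefore refuse every patient on the table, whereas reading 1 at SpO2 ≥88% refuses only the single cell 88% on FiO2 1.0.

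**The case against.** The best case for the text is that it never says the two limits are equivalent. They are joined by *or*, either one refuses, and a measured P/F below 100 always bars the lavage. That is correct, and it confines the problem to patients without a current gas, which is when Appendix G is meant to be used.

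Reading 2 may be the more natural sense of *imputed S/F (Appendix G)*, which would make the gap 89 against 100 rather than 57 against 100. The abbreviation list and section 9.6 support reading 1, so the wording is ambiguous; the mismatch remains on both.

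A third possibility is that 89 is a saturation floor on full oxygen, mislabelled. At FiO2 1.0, S/F 89 is SpO2 89%, the same number as the stopping rule, and section 9.6 writes that stopping rule as an S/F ratio. On that reading only the eight passing cells at FiO2 1.0 (SpO2 89–96%) are relevant, but the label and the table reference are wrong and the gate still has no usable imputed limb.

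Reference 17 may be the source of 89. Its figures are not in the documents, so it cannot be shown whether the number or the table reference is wrong. The claim here is only that the named table does not support the pair.

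The safeguards are real: pre-oxygenation, continuous monitoring, and termination for saturation below 89% for more than a minute, reported as an adverse event. The stopping rule, however, acts only after an aliquot has been instilled. Criterion 3i asks for PEEP above 8 where Appendix G asks for at least 8, so its use of the table is not perfectly tidy, but that does not affect the threshold argument.

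**Conclusion.** The point stands and should be fixed. That Appendix G does not support pairing 100 with 89 is certain from the table. The size depends on the reading: 65 of 66 cells admitted at SpO2 ≥88%, down to an imputed P/F of 57, if S/F is SpO2/FiO2; 16 conflicting cells at SpO2 ≥88% (26 overall) if the tabled value is meant.

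The counts describe the grid. The documents give no distribution of patients over it and no frequency of missing gases, so the number of lavages affected is unknown. No sample size, alpha or power figure changes. What is affected is a safety limit and, through it, which patients yield samples.

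**What to change.** In 5.1.2, 9.1 and 9.6, replace the S/F limb with: *or, if no current blood gas is available, Appendix G imputed P/F below 100*. The clinical team may prefer another threshold, provided one number applies to both measured and imputed P/F. Then:

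- State that the gate is read on the clinical FiO2, before the increase to 1.0.
- State what applies when the Appendix G conditions (such as SpO2 80–96% and PEEP ≥8) are not met, for example that a blood gas is required.
- As tidying, word the stopping rule in 9.6 as saturation below 89%, as in 5.1.2 and 9.1; at FiO2 1.0 the two are numerically the same.

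The cost is a wording amendment in three places. Some lavages that the present S/F limb allows would not be done; with ten patients per sequence, each refusal loses 1 of 10 biomarker samples for that group at that time point. A lower common threshold would keep more samples but would relax the limit for patients who have a measured gas.
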